6. ANALYSES AND SUMMARIES

The primary analysis will be conducted once all enrolled participants have completed Cycle 1 or have otherwise discontinued the study intervention. At this analysis, the primary endpoint of Grade ≥ 2 CRS rate during Cycle 1 and the safety endpoints will be evaluated.

For primary completion date reporting purpose (initial CSR), the full scope of the statistical analysis including all the endpoints will be conducted once all participants have been followed for response for at least 6 months or have otherwise discontinued response assessments within the first 6 months of treatment.

The final analysis will be conducted once the last participant enrolled will have been followed for OS for at least 2 years.

6.1. Primary Endpoints

The primary endpoint is Grade ≥ 2 CRS rate during Cycle 1, defined as the proportion of participants in the Safety Analysis Set experiencing Grade ≥ 2 CRS as assessed by ASTCT criteria.

Estimand strategy: All data collected after the intercurrent event of treatment discontinuation due to any reason will be excluded in the analysis.

Analysis set: Safety Analysis Set (as defined in [Section 4](#)).

Intercurrent events and missing data: The intercurrent event is treatment discontinuation due to any reason. No imputations for missing data will be performed.

Analysis methodology: The median and its corresponding 2-sided 90% credible interval based on the posterior distribution of Grade ≥ 2 CRS rate will be calculated. In addition, point estimates of Grade ≥ 2 CRS rate will be calculated along with the 2-sided 90% CIs using the Clopper-Pearson method⁸ (exact CI for a binomial proportion).

6.2. Secondary Safety Endpoint

6.2.1. Incidence of DLTs (Part 2A and Part 2C only)

DLT rate during the DLT observation period, which will be calculated as the number of DLT-evaluable participants with DLTs during the DLT observation period divided by the number of DLT-evaluable participants during the DLT observation period. Analyses of DLT will be performed on the DLT Evaluable Analysis Set (as defined in [Section 4](#)). DLT rate will be summarized and listed by dose levels.

6.3. Secondary Efficacy Endpoints

6.3.1. Objective Response Rate

ORR is defined as the proportion of participants with an objective response ([Section 3.2.1.1](#)) per IMWG response criteria as determined by investigator.

ORR will be analyzed in the Safety Analysis Set. Observed point estimate of ORR will be calculated along with the 2-sided 95% CIs using the Clopper-Pearson method.

The frequency (number and percentage) of participants with BOR by investigator in each response category and corresponding 2-sided 95% confidence interval will be summarized: sCR; CR; VGPR; PR; MR; SD; PD; Not evaluable (NE)/unknown.

In addition, the following response categories will be calculated along with corresponding 2-sided exact 95% CIs using the Clopper-Pearson method:

- VGPR or better (sCR + CR + VGPR);
- Clinical benefit (sCR + CR + VGPR + PR + MR).

BOR will be programmatically assessed based on reported timepoint responses by investigator recorded at evaluation time points from the date of first dose until confirmed disease progression using IMWG response criteria, death or start of new anticancer therapy, whichever occurs first. BOR by investigator needs to be confirmed according to IMWG response criteria (Table 4). If a participant meets multiple criteria in determining confirmed BOR, the order of criteria in this table will be used to define the hierarchy.

Twenty-eight days is required between the disease assessments however if done on the same day, a different sample is required for confirmation. A confirmatory response assessment may be performed >28 days following the initial response assessment, allowing for a maximum of 1 intervening missing or not evaluable assessment.

The rules for PD confirmation apply to both confirmed PD as BOR and confirmed PD after BOR (for time-to-event endpoint analyses), and the PD date is the date of the initial PD assessment.

Table 4. Derivation Rules for Confirmed Best Overall Response per IMWG Response Criteria

Scenario	Timepoint response at:			BOR
	Assessment 1	Assessment 2	Assessment 3	
1	sCR	sCR		sCR
2	sCR	NE	sCR	
3	CR/VGPR/PR/MR/SD/PD ^c	sCR	sCR	
4	CR	sCR/CR		CR
5	sCR/CR	CR		
6	CR	NE	CR	
7	VGPR/PR/MR/SD/PD ^c	CR	CR	
8	VGPR	sCR/CR/VGPR		VGPR
9	sCR/CR/VGPR	VGPR		
10	VGPR	NE	VGPR	
11	PR/MR/SD/PD ^c	VGPR	VGPR	
12	PR	sCR/CR/VGPR/PR		PR
13	sCR/CR/VGPR/PR	PR		
14	PR	NE	PR	
15	MR/SD/PD ^c	PR	PR	
16	MR	sCR/CR/VGPR/PR/MR		MR
17	sCR/CR/VGPR/PR/MR	MR		
18	MR	NE	MR	
19	SD/PD ^c	MR	MR	
20	SD	No further assessments		SD ^a

21	SD	sCR/CR/VGPR/PR/MR /SD/PD ^c	No further assessments	
22	sCR/CR/VGPR/PR/MR	NE/PD ^c or no further assessment	No further assessments	
23	PD ^c	sCR/CR/VGPR/PR/MR /SD	No further assessments	
24	PD ^c	PD (any reason) including PD after initiation of new anticancer therapy		PD
25	PD ^c	Participant died due to disease before further disease assessment (including death due to disease under study after initiation of new anticancer therapy)		
26	PD ^b	sCR/CR/VGPR/PR/MR /SD/NE/PD or no further assessments	No further assessments	
27	Death (due to disease under study) before initiation of new anticancer therapy			
28	Death (not due to disease under study)			NE
29	NE	No further assessment		
30	NE	NE/PD ^c	No further assessments	
31	PD ^c	NE	No further assessments	

EMD = extramedullary disease; IMWG = International Myeloma Working Group, sCR = stringent complete response, CR = complete response, PR = partial response, VGPR = very good partial response, SD = stable disease, PD = progressive disease, NE = not evaluable.
 
a. SD does not need to be confirmed.
 
b. PD due to EMD (includes any new lesion, increased extramedullary or paramedullary lesions, plasmacytomas), or bone marrow plasma cells does not need to be confirmed.
 
c. PD due to reasons other than EMD, or bone marrow plasma cells.
				

BOR by investigator will also be assessed programmatically based on derived responses per IMWG from the date of first dose until confirmed disease progression using IMWG response criteria, death or start of new anticancer therapy, whichever occurs first. This sensitivity analysis will follow the same rules as the secondary analysis except for deriving response based on the local laboratory and bone marrow data and the individual lesion data provided by the investigator.

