**Table 1. Schedule of Assessments: Part 1**

Visit Identifier	Screening	Treatment Period Cycle 1					Treatment Period (each 28 Day Cycle)		EOT Visit	FU Visit	LTFU Q12W	Notes/Protocol Section
		Day1	Day4	Day8	Day15	Day22	Cycles 2-6 Day1	Cycle7 Onwards Day1				
Visit Window	Day-28 to Day-1	-	-1/+3 D	-1/+3 D	±3D	±3D	±3D	±3D	1-4 Dpost- final dose	28 to 35 days post- final dose	±14D	
Disease response assessment (per IMWG criteria)							X	X	X	X*	X*	To be conducted on a 28-day (±1 wk) interval whether dose given or not (ie, the 28-day interval (±1 wk) from CID1 should be maintained regardless of dose delays/interruptions). See Section 8.1.  *For participants who discontinue study intervention without PD: perform at EOT visit, then at least Q4W (±1 wk) until PD, withdrawal of consent, participant lost to follow-up, death or defined end of study. For additional details on IMWG response criteria, see Appendix 10 .

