### 10.10. Appendix 10: IMWG Response Criteria for Multiple Myeloma

Participants must have measurable disease at enrollment (study entry) as defined by:

- Serum M-protein  $\geq 0.5$  g/dL (5 g/L);
- Urine M-protein  $\geq 200$  mg/24 hours;
- Serum FLC assay: involved serum FLC level  $\geq 10$  mg/dL, provided serum FLC ratio is abnormal.

Whenever more than 1 parameter is used to assess response, the overall assigned level of response is determined by the lowest level of response.

All response assessments will be entered on the CRF.

All response categories require 2 consecutive assessments made any time before starting new therapy. To confirm response or PD, 2 discrete samples are required and testing cannot be based upon the splitting of a single sample.

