**Table 16. Modified IMWG Response Criteria**

Response*	Modified IMWG Criteria
	at baseline, a 50% reduction in the size (SPD) of soft tissue plasmacytomas is also required. d
No Change/Stable Disease (SD)	
 
• Not meeting criteria for sCR, CR, VGPR, PR, MR or PD.
 

Progressive Disease (PD) b,c,f	
Any one or more of the following criteria:
 
 
• Increase of <math>\geq 25\%</math> from lowest confirmed response value in any 1 or more of the following:e,f 
 
Serum M-component (the absolute increase must be <math>\geq 0.5</math> g/d.L);
 
Serum M-protein increase <math>\geq 1</math> g/d.L, if the lowest M component was <math>\geq 5</math> g/d.L;
 
Urine M-protein (the absolute increase must be <math>\geq 200</math> mg/24 h).
 
 
 
In participants without measurable serum and urine M-protein levels, the difference between involved and uninvolved serum FLC levels (absolute increase must be <math>> 10</math> mg/d.L);
 
In patients without measurable serum and urine M-protein levels and without measurable involved serum FLC levels, CCI 
 
- <math>\geq</math> percentage irrespective of baseline status (absolute increase must be <math>\geq 0\%</math>)
 
 
 
• Appearance of a new lesion(s), <math>\geq 50\%</math> increase from nadir in SPD of <math>> 1</math> lesion, or <math>\geq 50\%</math> increase in the longest diameter of a previous lesion <math>> 1</math> cm in short axis.d
 
• <math>\geq 50\%</math> increase in circulating plasma cells (minimum of 200 cells per <math>\mu</math>L) if this is the only measure of disease
 

a All response categories require 2 consecutive assessments made any time before starting new therapy. Each category (except stable disease) will be considered unconfirmed until confirmatory test is performed. All categories (stable disease or better) require no known evidence of PD, new bone lesions or EM plasmacytomas if imaging studies were performed; imaging studies are not required to satisfy these response requirements except for requirement of FDG PET to confirm imaging plus MRD-negative.

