5.2.11. Nominal and Unscheduled Visits

For all algorithms and analyses, visit labels as specified on the CRF will be used as the nominal timepoint (ie, assessment will not be slotted).

Unless otherwise specified, unscheduled assessments will not be displayed in summary tables by nominal visit/timepoint. Unscheduled assessments will be used when deriving baseline and worst case on-treatment for safety analyses (except where noted for baseline ECGs). Additionally, unscheduled assessments will be used for efficacy analyses (eg, defining date of progression/censoring, best overall response, date of last contact).

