6.3.3. Duration of Response

DOR is defined, for participants with an objective response per IMWG criteria as determined by investigator, as the time from the first documentation of objective response that is subsequently confirmed, until confirmed PD per IMWG criteria, or death due to any cause, whichever occurs first. The rules for PD confirmation are described in [Table 4](#).

DOR will be calculated as follows:

$$\text{DOR (months)} = [\text{date of event or censoring} - \text{first date of objective response} + 1] / 30.4375$$

The censoring rules for DOR are as described for PFS in [Section 6.3.5](#) except that participants will not be censored for no adequate post-baseline assessment, as only participants with an objective response are included in the analysis of DOR.

If at least 3 participants achieve an objective response and subsequently have an event, DOR will be estimated using the same Kaplan-Meier method as described for PFS in [Section 6.3.5](#) and displayed graphically where appropriate. Otherwise only listings will be provided.

The DOR rate at 3, 6, 9, and 12 months (and in subsequent 6-month increments while there are participants still at risk) will be estimated with corresponding two-sided 95% CIs.

For sensitivity analyses on DOR, if $\geq 10\%$ of responders have died due to COVID-19 related reasons, these participants will be censored at the time of death.

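### SAP 6.3.1 accepts response confirmation on the same day or from 28 days on, but not 1–27 days later, against protocol Appendix 10 and the visit window

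*SAP*

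**What the plan says.** SAP 6.3.1 derives BOR by program from the investigator's timepoint responses and says confirmation follows the IMWG criteria as laid out in Table 4. Its timing paragraph then adds: "Twenty-eight days is required between the disease assessments however if done on the same day, a different sample is required for confirmation". The next sentence reads "A confirmatory response assessment may be performed >28 days following the initial response assessment" and tolerates one missing or non-evaluable assessment in between. Table 4 gives the order of assessments but no number of days.

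Protocol Appendix 10 states: "All response categories require 2 consecutive assessments made any time before starting new therapy". It adds: "To confirm response or PD, 2 discrete samples are required and testing cannot be based upon the splitting of a single sample". Footnote a of Table 16 repeats the timing rule and continues: "Each category (except stable disease) will be considered unconfirmed until confirmatory test is performed". Footnote e applies the same timing to PD. Protocol Section 8.1 asks for two consecutive assessments and names no interval.

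The disease response row of the Schedule of Assessments, counted from C1D1, says "To be conducted on a 28-day (±1 wk) interval whether dose given or not"; Parts 1 and 2 are the same. SAP 5.2.11 says that "unscheduled assessments will be used for efficacy analyses (eg, defining date of progression/censoring, best overall response, date of last contact").

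For progression, SAP 6.3.3 says "The rules for PD confirmation are described in" Table 4. SAP 6.3.4, 6.3.5 and 6.3.8 say the same.

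**The concern.** The SAP rule leaves a hole. It accepts a gap of 0 days with a second sample and a gap of 28 days or more, and it has no place for 1–27 days. The sentence on later confirmation covers only gaps above 28 days and does not close the hole. A programmer who codes the word used, which is a requirement, will reject a pair that Appendix 10 accepts.

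Two routes lead to such pairs. Scheduled visits within their windows can be less than 28 days apart, and an unscheduled repeat between visits, which the SAP admits for BOR, falls 1–27 days after the first result unless it is done on the same day.

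At stake are ORR, CRR and the BOR distribution. Two programmers could derive different response rates from the same data.

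For PD the text is only ambiguous. The endpoint sections refer to Table 4, which has no interval, so a promptly repeated PD is confirmed under its scenario 24. No bias in PFS, DOR or DOCR is claimed.

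**Working it through.** The documents give no figure for this point, so there is none to reproduce. The check compares the gaps each rule accepts with the gaps the schedule produces.

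**Gaps that confirm a response (two discrete samples, no new therapy)**

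| Gap between assessments | Protocol Appendix 10 | SAP 6.3.1, literal |
|---|---|---|
| 0 days | yes | yes |
| 1–27 days | yes | no |
| 28 days or more | yes | yes |

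**Gaps the schedule allows.** Let each assessment fall *d* whole days from its nominal day, with *d* from −7 to +7. For consecutive visits on the C1D1 grid, gap = 28 + d2 − d1.

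- Minimum: 28 − 14 = 14 days. Maximum: 28 + 14 = 42 days.
- First to third visit: at least 56 − 14 = 42 days.

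The SAP does allow for this window elsewhere. Its 70-day limit for PFS is explained in the version history as two cycles plus one week each, 2 × (28 + 7) = 70. The confirmation rule makes no such allowance.

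**Chance that a compliant pair is under 28 days apart.** The gap is below 28 when d2 < d1. If the two deviations are independent with the same distribution, P = [1 − P(d1 = d2)] / 2. The distribution is an assumption:

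| Assumed visit scatter | P(d1 = d2) | P(gap < 28) |
|---|---|---|
| every visit on its exact day | 1 | 0% |
| normal, SD 1 day, rounded to days, cut at ±7 | 0.271 | 36% |
| normal, SD 2 days, same treatment | 0.140 | 43% |
| uniform over ±7 days | 1/15 | 47% |

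This applies to a responder with exactly two in-response assessments. With three or more, the loss is zero if the first and third may be paired, since they are at least 42 days apart. SAP 6.3.1 mentions only a missing or non-evaluable assessment in between. If only adjacent visits may be paired, a three-assessment responder fails when both gaps are short. Under uniform scatter that is C(15,3)/15³ = 455/3375 = 13.5%.

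**Effect on ORR.** Each responder lost costs 1/30 = 3.3 points in a planned group of 30 (Part 1, or the RP2D group of 8 + 22) and 1/76 = 1.3 points overall. With *k* two-assessment responders, expected loss = k × P / N. Taking k = 1 to 3 (assumed) and P from SD 1 day to uniform:

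| N | k = 1 | k = 3 |
|---|---|---|
| 30 | 1.2–1.6 points | 3.6–4.7 points |
| 76 | 0.5–0.6 points | 1.4–1.8 points |

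**The case against.** The best defence is that nobody meant the literal rule. Accepting day 0 and day 28 but not day 14 makes no clinical sense, the same-day clause suggests that no hard minimum was intended, and 28 days is simply the visit interval. Table 4, named as the confirmation standard, has no interval for responses either. SAP 5.2.11 also says CRF visit labels serve as nominal timepoints, and on nominal days consecutive visits are exactly 28 days apart. Finally, the SAP may modify the protocol on secondary endpoints, and its version history records that text was added to 6.3.1 to clarify confirmation timing.

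Much of this is fair as to intent. It does not remove the conflict.

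- The sentence is phrased as a requirement, refers to confirmation and sits among rules to be programmed. Table 4's silence on days does not cancel an explicit sentence beside it.
- Nominal labels do not cover the unscheduled assessments that the same section admits for BOR, and SAP 5.2.8 uses the assessment date from the CRF.
- Nothing presents the interval as a deliberate departure from the protocol; 6.3.1 says that it follows IMWG.

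Two parts of the objection stand. The documents order an early repeat explicitly for suspected PD, not for response, so they do not show that short-gap response pairs will be frequent. The full analysis of all endpoints also waits for at least 6 months of response follow-up or earlier discontinuation of assessments (SAP Section 6). Two-assessment responders should therefore be mostly late responders and early failures or dropouts.

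**Conclusion.** The concern holds. As written, the timing sentence in SAP 6.3.1 conflicts with protocol Appendix 10 and with the ±1 week visit window, and if followed literally it can misclassify a confirmed response as unconfirmed.

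It is a minor point. The size is uncertain and probably small: nil if visits fall on their exact days, or if later in-response assessments can serve as confirmation. The upper figure of 4.7 points needs three two-assessment responders in a group of 30 and uniform visit scatter, neither of which the documents support or exclude. Confidence is high in the conflict and low in the magnitude.

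**What to change.** Replace the two sentences of the timing paragraph in SAP 6.3.1 with text to this effect:

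> No minimum interval is required between the initial and the confirmatory assessment. Two discrete samples are required, including when both assessments fall on the same day. At most one missing or non-evaluable assessment may lie between them.

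Add one sentence: PD confirmation follows Table 4 with no minimum interval, in line with protocol Appendix 10.

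If the sponsor does want a minimum interval for responses, the SAP should declare it as a departure from Appendix 10, state how gaps of 1–27 days are handled, and allow for the visit window.

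The cost is three sentences in the SAP and the matching line of the BOR program. No new data are needed.

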6.3.7. Time to Response

TTR is defined, for participants with an objective response per IMWG criteria as determined by investigator, as the time from the date of first dose to the first documentation of objective response that is subsequently confirmed. For participants with EMD at baseline, MR or better (for those with target plasmacytomas) and CR or better (for those with non-target non-bone EMD only) cannot be confirmed until a post-baseline EMD assessment is performed and the date of confirmed response cannot be prior to the initial EMD assessment date. TTR will be calculated in weeks as follows:

$$\text{TTR (weeks)} = (\text{date of first objective response} - \text{date of first dose} + 1) / 7$$

Time to VGPR (TTVGPR) and time to CR (TTCR) are defined similar to TTR but for participants with BOR of VGPR or better and sCR/CR, respectively.

TTR, TTVGPR, and TTCR will be summarized using simple descriptive statistics.

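### Across one not-evaluable visit, SAP Table 4 confirms a response only by the identical category; read literally, a response that deepens over the gap is dated late or not counted

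*SAP*

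**What the plan says.** SAP 6.3.1 makes Table 4 the operative rule: "BOR by investigator needs to be confirmed according to IMWG response criteria (Table 4"). Ties are settled by table order: "If a participant meets multiple criteria in determining confirmed BOR, the order of criteria in this table will be used to define the hierarchy". The paragraph above the table permits a later confirmation, "allowing for a maximum of 1 intervening missing or not evaluable assessment", with no condition on which category the later assessment shows.

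Table 4 treats two situations differently:

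- **Adjacent visits.** An equal or deeper second response confirms the first (rows 4, 8, 12, 16). Row 12, for example, reads "12 PR sCR/CR/VGPR/PR" and gives PR. A shallower second response confirms at the shallower level (rows 5, 9, 13, 17).
- **One NE between.** Only rows 2, 6, 10, 14 and 18 apply: sCR-NE-sCR, CR-NE-CR, VGPR-NE-VGPR, PR-NE-PR and MR-NE-MR.

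Row 22 is the fallback for an unconfirmed response. A response followed by "NE/PD ^c or no further assessment", with nothing after that, gives SD.

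Two endpoints take their date from confirmation. TTR (SAP 6.3.7) ends at "the first documentation of objective response that is subsequently confirmed". DOR (SAP 6.3.3) is defined "as the time from the first documentation of objective response that is subsequently confirmed". For the assessment interval, the protocol schedule (Table 1) says "To be conducted on a 28-day (±1 wk) interval whether dose given or not". Protocol 8.1 and Appendix 10 require two assessments in a row for confirmation and say nothing about an NE in between.

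**The concern.** An NE visit carries no information against a response. If a VGPR at the next visit is good enough to confirm a PR, the SAP gives no reason why the same VGPR should fail to confirm it after one uninformative visit. The sentence above the table suggests that it should confirm; the rows of the table do not include it.

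BOR is assigned by program, so the difference reaches the output. A program that follows the rows and one that follows the sentence can produce different ORR, CRR, TTR, DOR and DOCR from the same data. The participants affected are those whose response deepens across a gap. The sensitivity analysis in 6.3.1, on responses derived from laboratory and lesion data, uses the same confirmation rules and so would not show the problem.

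There is a related gap. The sentence treats missing and NE assessments alike, while the table lists only NE. If a missed visit leaves no record, a program could treat PR-(missing)-VGPR as adjacent and confirm it under row 12, yet not confirm PR-NE-VGPR.

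**Working it through.** The plan states no figure for this rule, so the check is an enumeration of Table 4 followed by date arithmetic.

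**1. Which pairs confirm.** Take the five categories sCR, CR, VGPR, PR and MR, which form 5 × 5 = 25 ordered pairs.

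| Pairs | Adjacent | One NE between |
|---|---|---|
| All 25 | 25 confirm | 5 confirm (identical only) |
| PR or better, second equal or deeper (4 + 6 = 10) | 10 confirm | 4 confirm |

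**2. What happens to individual sequences.** Rows are applied literally to successive visits, in table order.

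| Sequence | BOR | Response dated at |
|---|---|---|
| PR-VGPR | PR (row 12) | visit 1 |
| PR-NE-PR | PR (row 14) | visit 1 |
| PR-NE-VGPR-VGPR | VGPR (row 8) | visit 3 |
| PR-NE-VGPR-PR | PR (row 13) | visit 3 |
| PR-NE-VGPR, nothing further | SD (row 22) | no response |
| PR-NE-VGPR-PD, nothing further | SD (row 22) | no response |
| PR-NE-VGPR-PD-PD | PD (row 24) | no response |

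The PD in the last two lines is the type that needs confirmation (footnote c). If an equal or deeper response could confirm across the NE, all the PR-NE-VGPR sequences would be responses dated at visit 1.

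**3. Size of the redating.** Visit 1 to visit 3 is 2 × 28 = 56 days.

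- TTR: 56 / 7 = 8.0 weeks longer.
- DOR: 56 / 30.4375 = 1.84 months shorter.

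**4. Size of a lost responder.** One participant is 1/76 = 1.3 points of ORR at the planned total, and 1/30 = 3.3 points in a 30-participant group.

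**5. CRR and DOCR.** CR-NE-sCR and sCR-NE-CR match no confirming row. With nothing further, neither counts towards CRR. In CR-NE-sCR-sCR, row 1 gives sCR, but DOCR starts at visit 3 instead of visit 1.

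**6. How many participants.** The documents give neither the NE rate p nor the share q of responders who reach VGPR within two visits of their first PR, so both are assumed. Redating needs an NE at the visit after the first PR, an evaluable visit after that, and deepening by then:

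share redated ≈ p × (1 − p) × q

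If deepening takes one, two or three visits with equal chance, q = 2/3.

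| p | p × (1 − p) × 2/3 | Simulation, 20,000 responders per rate | Simulation, 40,000 responders, 12 visits |
|---|---|---|---|
| 5% | 3.2% | 3.2% | 3.1% |
| 10% | 6.0% | 6.3% | 5.8% |
| 15% | 8.5% | 8.5% | 8.4% |

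Even if all 76 participants responded, this would be 0.032 × 76 = 2.4 to 0.085 × 76 = 6.5 people redated. Responders lost altogether were 0.2% to 0.5% in the first simulation, or at most 0.002 × 76 = 0.15 to 0.005 × 76 = 0.38 of a person. The second simulation, with full 12-visit follow-up, lost none. Loss requires assessments to stop early.

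**The case against.** The strongest reply is that Table 4 omits these sequences and does not reject them. No row says that PR-NE-VGPR is unconfirmed. The sentence above the table, read together with row 12, supports confirming it as PR, and the protocol's criteria contain no same-category requirement. This stands in part. A reader might infer that the SAP flatly contradicts itself or forbids such a confirmation, and the text does not go that far. But the sentence and the rows can be programmed differently, and the rows are what 6.3.1 cites for confirmation.

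A reader might also infer that PR-NE-VGPR-PD always yields SD. It does not. SD follows only if row 22 is applied to visits 3 and 4, which the SAP does not spell out, and only if nothing comes after the PD. Protocol 8.1.1 asks for suspected PD to be retested, and a confirmed PD gives BOR PD by row 24. Under either outcome the participant is not a responder.

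It is also tempting to say that missed 24-hour urine collections make NE visits common and that responses usually deepen early. The documents support neither statement. Protocol 8.1.1 asks for a second urine collection within 7 days and limits UPEP for participants without measurable urine disease at baseline. SAP 5.2.11 lets unscheduled assessments count for efficacy. Responders who stay at PR, or who first appear at VGPR and hold it, are unaffected, so q may be well below 2/3.

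Finally, loosening the rule now can only add responses or move them earlier. The study is open-label and protocol 4.1 reports enrollment complete, so a change needs a recorded reason.

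**Conclusion.** The point holds as a minor defect in the derivation rule. Table 4 is narrower across one NE than at adjacent visits, and narrower than the sentence that introduces it. For a participant whose response deepens over the gap, a literal derivation either delays the response date by 56 days nominal or leaves the response uncounted.

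The number of participants is small. About 3% to 8% of responders would be redated if NE occurs at 5% to 15% of visits and PR deepens to VGPR in one to three visits. Both conditions are assumptions. The expected number lost is below one participant, so a reading that ORR is materially understated is not supported.

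The affected endpoints (ORR, CRR, TTR, DOR, DOCR) are secondary and summarized without formal testing. The primary Grade ≥2 CRS rate and its decision rule do not use Table 4.

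**What to change.** Before database lock, amend SAP Table 4 as follows:

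- Extend rows 6, 10, 14 and 18 so that the assessment after one NE may be the same category or deeper. For example, PR, NE, then sCR/CR/VGPR/PR gives PR. Row 2 needs no change, since nothing is deeper than sCR.
- Add the reverse-order equivalents of rows 5, 9, 13 and 17. For example, sCR, NE, CR gives CR.
- State that one missing assessment is handled in the same way as one NE.
- Record the rationale and the date of the change, because the study is open-label.

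The cost is a few table rows and the matching program edits. The downside is slightly more permissive confirmation. Reporting ORR, CRR, TTR, DOR and DOCR under the identical-category version as well would show how much it matters. If the sponsor intends the identical-category rule, the sentence in 6.3.1 should say so; that removes the ambiguity but keeps the late dating.
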